16.5 Data & Safety Monitoring

- 16.51 The principal investigator(s) and the study statistician will review the study at least twice a year to identify accrual, AE, and any endpoint problems that might be developing. The Mayo Clinic Cancer Center (MCCC) Data Safety Monitoring Board (DSMB) is responsible for reviewing accrual and safety data for this trial at least twice a year, based on reports provided by the MCCC Statistical Office.
- 16.52 Adverse Event Stopping Rules: The stopping rules specified below are based on the knowledge available at study development. We note that the AE Stopping Rule may be adjusted in the event of either (1) the study re-opening to accrual or (2) at any time during the conduct of the trial and in consideration of newly acquired information regarding the AE profile of the treatment(s) under investigation. The study team may choose to suspend accrual because of unexpected AE profiles that have not crossed the specified rule below.
- 16.521 Safety Cohort: By the nature of the "cohorts of three" safety portion, stopping rules are in place for dose level of Venetoclax. Specifically, if 2 or more significant toxicities are observed during cycle 3 at the given dose level, accrual to that dose level will be stopped, and patients will be accrued to the next lower dose level until a maximum of 6 patients are treated at the lower level. Note that significant toxicities that affects dose de-escalation is only that which is observed in the first three cycles of treatment. However, all cycles will be reviewed, and the study team will determine whether the dose level needs to be adjusted for future patients if patients experience a Grade 4 or higher non-hematologic adverse event over all cycles at any given dose level unless it is considered definitely unrelated to treatment.
- 16.522 Expansion Cohort: Accrual will be temporarily suspended to this study as documented below in both the safety run in and the full study population if at any time, we observe events considered at least possibly related to study treatment (i.e. an AE with attribute specified as "possible," "probable," or "definite") that satisfy one of the following:
 - If 4 or more patients in the first 12 treated patients experience a grade 4 non-hematologic AE at least possibly related to treatment
 - If after the first 12 patients have been treated, 30% of all patients experience a grade 4 non-hematologic AE at least possibly related to treatment.
 - If 4 or more patients in the first 12 patients require discontinuation of therapy due to grade 3-4 hematologic AE of at least possibly related to

treatment

- If after the first 12 patients are treated 30% of all patients require discontinuation of therapy due to grade 3-4 hematologic AE
- If 2 patients experienced a grade 5 AE, at least possibly related to treatment.

We note that we will review grade 4 and 5 AEs deemed "unrelated" or "unlikely to be related", to verify their attribution and to monitor the emergence of a previously unrecognized treatment-related AE.

Note: If safety analysis fails in first 6 patients, those patients will not be used to evaluate the stopping rule. in expansion cohort.

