- 1. Since cycle length is 30 days, rituximab and hyaluronidase human maintenance is given once every other cycle. A total of 6 rituximab and hyaluronidase human treatments during the maintenance phase.
- 2. A +/- 7 day window is allowed for day 1 of treatment during maintenance. NOTE: No polatuzumab vedotin will be administered.
- 3. All subjects who get a dose reduction of Venetoclax during induction, will be maintained on the same corresponding dose in maintenance.
 - * If 400 mg days 1-21 is not tolerated in the *safety run-in*, venetoclax will be given 400 mg days 1-10.
- 4. For Venetoclax dose reductions in Maintenance refer to Table 8.21.
- 7.4 For this protocol, the patient must return to the consenting ACCRU institution for CBC evaluation, or have outside laboratory CBC every 7 days during the first 6 weeks of therapy, every 30 days during maintenance, and every 3 months during clinical follow-up (Active Monitoring Phase).

- 7.5 Study treatment by a local medical doctor (LMD) is not allowed.
- 7.6 Safety Portion: Rules for Dose De-escalation

Dose de-escalation will be considered if the initial safety portion dose level (venetoclax 400 mg days 1-21) per Table 7.2a proves excessively toxic, with 2 or more subjects having excessive significant toxicity as defined in Section 7.7. Dose de-escalation will proceed per section 7.6.1.

7.61 The first cohort of three patients will be treated at the starting dose level of Venetoclax (400 mg days 1-21) and observed for at least 63 days (3 cycles) from the start of treatment to assess toxicity. If significant toxicity as defined in Section 7.7 is observed in 0 or 1 of these 3 patients, 3 new patients will be accrued and treated at same dose level of Venetoclax (400 mg days 1-21) and observed for 3 cycles. After enrolling 6 patients on Venetoclax dose level of 400 mg days 1-21, if ≤1 patient experience significant toxicity, then this dose will be considered safe and the rest of the patients in expansion cohort will be treated at this dose level of Venetoclax. However, if 2 or more out of the first 3 or 6 patients experience significant toxicity, then the dose of venetoclax may be descalated to 300mg days 1-21. In this case, another safety analysis using similar 3+3 design approach will be conducted at the reduced dose level of venetoclax.

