16.2 Statistical Design

- 16.21 Decision Rule: The largest success proportion where the proposed treatment regimen would be considered ineffective in this population is 15%, and the smallest success proportion that would warrant subsequent studies with the proposed regimen in this patient population is 35%. The following one-stage design with an interim analysis is based on a two-stage Simon optimum design² and requires 46 evaluable patients to test the null hypothesis that the true success proportion in this patient population is at most 15%.
 - 16.211 Interim Analysis: Enter 16 evaluable patients into the study. If 3 or fewer successes are observed in the first 16 evaluable patients, we will consider this regimen ineffective in this patient population and terminate the study. Otherwise, if the number of successes is at least 4, we will continue accrual.
 - 16.212 Final Decision Rule: Enter an additional 30 evaluable patients into the study. If 10 or fewer successes are observed in the first 46 evaluable patients, we will consider this regimen ineffective in this patient population and terminate the study. Otherwise, if the number of success is at least 11, this will be considered evidence of promising activity and the treatment may be recommended for further testing in subsequent studies in this population.
 - 16.213 Over Accrual: If more than the target number of patients are accrued, the additional patients will not be used to evaluate the stopping rule or used in any decision-making process. Analysis involving over accrued patients is discussed in section 16.313.

NOTE: We will not suspend accrual at the interim analysis to allow the first 16 patients to become evaluable, unless undue toxicity is observed. Given the limited overall sample size and the inclusion of an AE stopping rule, we feel it is ethical to not halt accrual for the interim analysis. However, if accrual is extremely rapid, we may temporarily suspend accrual in order to obtain safety data on these patients before reopening accrual to further patients.

- 16.214 Dose de-escalation in safety analysis: A safety analysis will be performed in the first 6 evaluable patients per Section 16.4. In the case of unacceptable toxicity, the dose will be de-escalated. If this occurs, the first 6 patients will be evaluated separately and will not be included in any decision-making criteria.

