16.4 Early Safety Analysis

The first cohort of three patients will be treated at the starting dose level of Venetoclax (400 mg days 1-21) and observed for at least 63 days (3 cycles) from the start of treatment to assess toxicity. If significant toxicity as defined in section 7.7 is observed in 0 or 1 of these 3 patients, 3 new patients will be accrued and treated at same dose level of Venetoclax (400 mg days 1-21) and observed for 3 cycles. After enrolling 6 patients on Venetoclax dose level of 400 mg days 1-21, if \leq 1 patient experience significant toxicity, then this dose will be considered safe and rest of the patients in expansion cohort will be treated at this dose level of Venetoclax.

However, if 2 or more out of the first 3 or 6 patients experience significant toxicity, then the dose of venetoclax may be de-escalated to 300 mg days 1-21 (Dose Level -1, Table 8.21). In this case, another safety analysis using similar 3+3 design approach will be conducted at the reduced dose level of venetoclax.

Safety will be assessed through summaries of adverse events and changes from baseline laboratory results. All adverse events occurring on or after first study treatment will be summarized by NCI CTCAE v5.0 grade. Deaths reported during the treatment period and during post-treatment follow-up will be listed and summarized.

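### The 7.713 neutropenia NOTE and the Table 7.3 fallback dose each contradict other current text; the 16.521 trigger is only loosely worded

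*Combined protocol and SAP*

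**What the plan says.** **Run-in rule.** Sections 7.61 and 16.4 treat three patients, then three more, at venetoclax 400 mg days 1-21, each observed for three cycles. With at most one affected patient in six, 16.4 reads "patient experience significant toxicity, then this dose will be considered safe". The opposite branch applies "if 2 or more out of the first 3 or 6 patients experience significant toxicity". For that branch 16.4 names the fallback in these terms: "then the dose of venetoclax may be de-escalated to 300 mg days 1-21 (Dose Level -1, Table 8.21". Section 7.6 uses the same unit: "with 2 or more subjects having excessive significant toxicity as defined in Section 7.7".

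**The stopping-rule section.** Section 16.521 says that "if 2 or more significant toxicities are observed during cycle 3 at the given dose level, accrual to that dose level will be stopped". Its next sentence is "Note that significant toxicities that affects dose de-escalation is only that which is observed in the first three cycles of treatment".

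**What counts as toxicity.** Section 7.713 lists, with no condition on fever, Grade 4 neutropenia that persists beyond 7 days when no growth factor is given. A NOTE two bullets down says that non-febrile Grade 4 neutropenia is not a significant toxicity and should lead to growth factor on later doses. The NOTE has no limit on duration.

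**Fallback dose.** Footnote 3 of Table 7.2a refers the induction fallback to 7.61, which gives 300 mg days 1-21, as does 16.4. Table 8.21 covers induction and maintenance by its title, lists 300 mg days 1-21 as a starting dose, and has only days 1-21 levels. The asterisk under Table 7.3 (maintenance) instead gives 400 mg days 1-10 if the run-in dose is not tolerated. Footnote 3 of that table carries an induction reduction into maintenance, and footnote 4 points to Table 8.21. Section 7.0 says the safety portion determines the *frequency* of venetoclax.

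**The concern.** The run-in result does more than choose a dose. Under 16.214 and 16.311, patients treated at a dose that is later reduced are left out of the phase II decision rules, and 16.22 then adds six more evaluable patients. The definition of a countable event should therefore give one answer for one set of data. For prolonged afebrile neutropenia it gives two, and the NOTE errs toward clearing the higher dose. Neutropenia is a relevant event for this regimen: Section 1.231 reports Grade 3 or higher neutropenia in 38% of patients on single-agent polatuzumab vedotin.

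The asterisk does not touch the run-in decision or the primary endpoint, which is read at the end of induction. After a failed run-in, however, it would leave sites with two maintenance regimens for responding patients, in the period over which maintenance response and much of PFS are observed.

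**Working it through.** The documents give no operating characteristics for the run-in, so there is no stated figure to reproduce on this point. As a background check, the design in 16.2 was recomputed as P(at least 4 successes in 16 and at least 11 in 46). It gives 0.0486 at 15% and 0.8506 at 35%, against the 0.049 and 0.851 in 16.24. Those figures stand.

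**A. Section 7.713, Grade 4 neutropenia without growth factor**

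| Episode | Bullet | NOTE |
|---|---|---|
| Afebrile, 7 days or less | not counted | excluded |
| Afebrile, more than 7 days | counted | excluded |
| Febrile, more than 7 days | counted | not addressed |

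Only the middle row conflicts. Suppose two of six patients have such an episode and nobody has another significant toxicity. Under the bullet the count is 2/6, which meets the de-escalation rule. Under the NOTE it is 0/6, and 400 mg is cleared. This case needs no assumed rates.

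For scale only, with rates that are assumed: let o be the per-patient rate of other significant toxicity and r the rate of prolonged afebrile Grade 4 neutropenia. The rule clears the dose with probability (1-p)^6 + 6p(1-p)^5, where p = o under the NOTE and p = o + (1-o)r under the bullet. With o = 0.15 and r = 0.05, p = 0.15 + 0.85 × 0.05 = 0.1925, and the bullet gives 0.277 + 0.397 = 0.674.

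| o | NOTE | Bullet, r = 2.5% | Bullet, r = 5% |
|---|---|---|---|
| 10% | 0.886 | 0.839 | 0.788 |
| 15% | 0.776 | 0.726 | 0.674 |
| 20% | 0.655 | 0.606 | 0.558 |

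Over this range the chance of clearing 400 mg differs by about 5 to 10 percentage points.

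**B. Maintenance after a failed run-in, for a patient who started at 300 mg and was not reduced**

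- Daily dose: 400/300 - 1 = 33% higher under the asterisk.
- Cycle total: 400 × 10 = 4,000 mg against 300 × 21 = 6,300 mg; 4,000/6,300 - 1 = -37%.
- Twelve cycles: 48,000 against 75,600 mg.

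The two texts describe different regimens, and Table 8.21 has no days 1-10 level from which the asterisk could have been drawn.

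**C. Section 16.521**

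The number of toxicities can never be smaller than the number of patients with at least one. Over the same three cycles, an event count of 2 is therefore reached no later than a patient count of 2. The rules part when one patient of six has two significant toxicities: one patient clears the dose under 16.4, two toxicities stop it under 16.521. The reverse cannot happen.

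**The case against.** **On A.** The NOTE sits directly under the febrile neutropenia bullet and may be meant only to clarify it, leaving the bullet on prolonged neutropenia to stand. The disputed case should also be uncommon. Sections 4.0 and 7.4 require weekly blood counts for the first six weeks, Table 8.31 starts G-CSF in the current cycle, and 7.713 allows prophylactic growth factor for marrow infiltration. This stands as to frequency, but it does not remove the conflict. The NOTE states no such limit and speaks of later doses, and the general growth-factor allowance applies after cycle 2 or after earlier neutropenia. A first prolonged episode in cycles 1-2 remains possible.

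**On B.** A reader might infer that 7.0 also prescribes 400 mg days 1-10. It states no regimen, and its preceding sentence speaks of confirming the *dose*. A reader might also infer that patients cut to 200 or 100 mg in induction would go back up to 400 mg, a two- or four-fold daily increase. Footnote 3 and the ban on re-escalation in 8.0 hold those patients at their reduced dose. Nor do the documents show that the asterisk regimen is more toxic: its daily dose is higher, but its cycle total is lower.

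**On C.** Section 16.521 opens by referring to the cohorts-of-three design and is best read as shorthand for 7.61 and 16.4. Read alone, its cycle 3 wording might suggest that earlier toxicity is ignored; the next sentence rules that out. A reader might also make something of the verbs: 16.214 says "In the case of unacceptable toxicity, the dose will be de-escalated" and 16.521 says "and patients will be accrued to the next lower dose level until a maximum of 6 patients", while 7.61 and 16.4 use *may*. That is largely a drafting preference. No text provides for continuing at 400 mg after two affected patients, and *may* is compatible with terminating the study under 16.25.

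**Conclusion.** Two rules are wrong as written. The 7.713 NOTE excludes an event that the bullet counts, so identical run-in data can give 2/6 or 0/6 and opposite dose decisions. The case should be uncommon, but the error under the NOTE runs toward clearing 400 mg. The Table 7.3 asterisk contradicts 7.61, 16.4 and Table 8.21. It matters only if the run-in fails, and then mainly for patients who start at 300 mg and are not individually reduced, since footnote 3 does not clearly cover them.

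The 16.521 wording is minor, because it errs only toward stopping once the three-cycle window is applied. The fixed cases and the dose arithmetic rest on the text alone; the 5 to 10 points under A depend on assumed rates. It would be wrong to infer any defect in the phase II sample size, alpha or power.

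**What to change.** 1. **7.713:** limit the NOTE to non-febrile Grade 4 neutropenia lasting 7 days or less.
2. **Table 7.3:** replace the asterisk text with 300 mg days 1-21, stating that patients reduced further in induction stay at their own level under footnote 3. In 7.0, change *frequency* to *dose*.
3. **16.521 (minor):** make the trigger two or more patients with at least one significant toxicity in cycles 1-3, to match 7.6, 7.61 and 16.4.

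The cost is a wording amendment. It needs no extra patients or procedures and no change to the sample size.

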16.6 Results Reporting on ClinicalTrials.gov

At study activation, this study will have been registered within the "ClincialTrails.gov" website. The Primary and Secondary Endpoints along with other required information for this study will be reported on For purposes of timing of the Results Reporting, the initial estimated completion date for the Primary Endpoint of this study is 2.5 years after the study opens to accrual. The definition of "Primary Endpoint Completion Date" (PECD) for this study is at the time all patients registered have achieved a confirmed complete response during induction or have completed induction treatment without achieving a confirmed complete response.

16.7 Subset Analysis for Minorities

- 16.71 Study availability: This study will be available to all eligible patients, regardless of gender, race or ethnic origin.
- 16.72 Statistical analysis by subset: There is no information currently available regarding differential effects of this regimen in subsets defined by race, gender, or ethnicity, and there is no reason to expect such differences to exist. Therefore, although the planned analysis will, as always, look for differences in treatment effect based on racial and gender groupings, the sample size is not increased in order to provide additional power for subset analyses.
- 16.73 Regional population: The geographical region served by MCCC has a population which includes approximately 5% minorities. Based on prior MCCC studies involving similar disease sites, we expect about 5-7% of patients will be classified as minorities by race and about 25% of patients will be women.

Accrual Estimates by Gender/Ethnicity/Race

Ethnic Category	Sex/Gender				
	Females	Males	Unknown	Total	
Hispanic or Latino	1	3	0	4	
Not Hispanic or Latino	15	44	0	59	
Ethnic Category: Total of all Patients *	16	47	0	63	
Racial Category					
American Indian or Alaskan Native	0	0	0	0	
Asian	0	0	0	0	

Black or African American	1	4	0	5
Native Hawaiian or other Pacific Islander	0	0	0	0
White	15	43	0	58
Racial Category: Total of all Patients*	16	47	0	63

Ethnic Categories:

Hispanic or Latino – a person of Cuban, Mexican, Puerto Rican, South or Central American, or other Spanish culture or origin, regardless of race. The term "Spanish origin" can also be used in addition to "Hispanic or Latino."

Not Hispanic or Latino Racial Categories:

American Indian or Alaskan Native – a person having origins in any of the original peoples of North, Central, or South America, and who maintains tribal affiliations or community attachment.

Asian – a person having origins in any of the original peoples of the Far East, Southeast Asia, or the Indian subcontinent including, for example, Cambodia, China, India, Japan, Korea, Malaysia, Pakistan, the Philippine Islands, Thailand, and Vietnam. (Note: Individuals from the Philippine Islands have been recorded as Pacific Islanders in previous data collection strategies.)

Black or African American – a person having origins in any of the black racial groups of Africa. Terms such as "Haitian" or "Negro" can be used in addition to "Black or African American."

Native Hawaiian or other Pacific Islander – a person having origins in any of the original peoples of Hawaii, Guam, Samoa, or other Pacific Islands.

White – a person having origins in any of the original peoples of Europe, the Middle East, or North Africa.

17.0 Pathology Considerations/Tissue Biospecimens

17.1 Tissue Biospecimen Submission

NOTE: Patients must have consented to submission of the optional tissue(s) listed in the following table.

17.11 Summary Table of Tissue Biospecimens for This Protocol

Type of tissue biospecimen to submit	Mandatory or optional	When to submit
Formalin-fixed paraffin- embedded (FFPE) tissue blocks with corresponding H&E (OR unstained slides with corresponding H&E)	Mandatory	Within 30 days of registration
Viably cryopreserved core needle biopsy	Optional	Within 30 days of registration
Formalin-fixed paraffin- embedded (FFPE) tissue blocks with corresponding H&E (OR unstained slides with corresponding H&E)	Optional	End of cycle 1
Viably cryopreserved core needle biopsy	Optional	End of cycle 1
Formalin-fixed paraffin- embedded (FFPE) tissue blocks with corresponding H&E (OR unstained slides with corresponding H&E)	Optional	Progression

Viably cryopreserved core needle biopsy	Optional	Progression

NOTE: Viably cryopreserved core needle biopsy is preferred when possible. However, FFPE and/or viably cryopreserved core needle biopsies will be accepted.

- 17.2 All Diagnostic Slides from initial and relapse confirmatory biopsy original and/or recurrent tissue
 - 17.2.1 Paraffin Embedded Tissue Blocks/Slides
 - 17.2.1.1 Submit one formalin fixed paraffin embedded (FFPE) tumor tissue block with largest amount of invasive tumor (at least 1 cm of tumor for cases of surgical resection) (from original and recurrent) surgery. Please submit biopsy material from each surgery if available. Submission of materials from at least one biopsy is required.
 - 17.2.1.2 The FFPE tissue block is preferred; however, if an institution is unable to provide a tissue block, cut 15 five-micron sections and mount on charged glass slides. Label the slides with ACCRU patient ID number, accession number, and order of sections. The unstained slides will be processed as described in 17. Ideally, each slide must have a minimum of 75% tumor tissue on the slide to be deemed adequate for study. Do not bake or place covers slips on the slides.
 - 17.2.1.3 The following materials below are mandatory (unless indicated otherwise) and required for shipment:
 - Paraffin embedded tissue blocks OR 15 unstained slides
 - Research Tissue Specimen Submission Form
 - Surgical Pathology Report

Note: Please include the ACCRU patient ID number on all materials listed above. Please do not place sticky labels on slides.

- 17.2.1.4 The block/slides must be appropriately packed to prevent damage (e.g., slides should be placed in appropriate slide container) and placed in an individual plastic bag. Label the bag with the protocol number, ACCRU patient ID number, and patient initials.
- 17.2.1.5 Tissue specimens must be shipped \leq 30 days after registration.
- 17.2.1.6Verify that the appropriate sections of the Tissue Specimen Submission Form are completed and filled in correctly. Enter information from the Tissue Specimen Submission Form into the remote data entry system on the same day the specimen is submitted (see Forms Packet).
- 17.2.1.7 Ship all **block/slide tissue specimens** and accompanying materials to the ACCRU Research Base (**no frozen tissue**):

ACCRU Operations Office

- 17.2.1.8 Assessment of tissue quality will occur at the time the translational studies are performed.
- 17.2.1.9 After the pathologist assesses the tissue quality, the block and appropriate paperwork will be returned to the ACCRU Operations Office.
- 17.2.1.10 When an appropriate request is submitted, the ACCRU Operations Office will forward the block/slides to the ACCRU Research Base PRC Shared Resource, [name], Mayo Clinic Rochester (Attn: PRC Supervisor) for processing as outlined in Section 17.

